SOC	system organ class
SPEP	serum M-protein quantitation by electrophoresis
TEAE	treatment emergent adverse event
UPEP	urine M-protein quantitation by electrophoresis
VGPR	very good partial response
WBC	white blood cell

1. INTRODUCTION

This statistical analysis plan (SAP) contains definitions of analysis sets, derived variables, and statistical methods for all planned analyses for study JNJ54767414SMM2001. The QTc substudy analysis and reporting will be conducted by an external vendor.

1.1. Trial Objectives

The primary objectives are:

- To evaluate if daratumumab can effectively decrease M protein in subjects with intermediate or high-risk smoldering MM (SMM) as assessed by CR rate
- To determine if daratumumab reduces the progression/death rate in subjects with intermediate or high-risk SMM

The secondary objectives are:

- To evaluate preliminary efficacy, including Overall Response Rate (ORR) and PFS
- To evaluate the MRD negative rate
- To evaluate the pharmacokinetics and immunogenicity of daratumumab
- To assess the safety profile of daratumumab given in 3 different dosing schedules
- To determine if daratumumab has an effect on QT interval

1.2. Trial Design

This is a randomized, open-label, 3-arm, multicenter study in subjects at least 18 years old with intermediate or high-risk SMM. Randomization will be stratified based on the number of risk factors for progression to symptomatic MM (<2 vs ≥ 2). Approximately 120 subjects will be enrolled in this study with 40 subjects planned per treatment arm.

Subject participation will include a Screening Phase, a Treatment Phase, and a Follow up Phase. The Screening Phase will be up to 28 days before Cycle 1, Day 1. Treatment cycles are 8 weeks in length. For subjects randomized to Arm A or Arm B, the Treatment Phase will extend from Cycle 1 to Cycle 20. In Arm A, daratumumab will be administered weekly in Cycle 1, every other week in Cycle 2 and Cycle 3, every 4 weeks in Cycle 4 to Cycle 7, and from Cycle 8 to Cycle 20 on Day 1 of each cycle. In Arm B, daratumumab will be administered weekly in Cycle 1 and then on Day 1 of each cycle from Cycle 2 to Cycle 20. For subjects randomized to Arm C, the Treatment Phase consists of Cycle 1 only, when daratumumab will be administered weekly.

Measures to prevent infusion related reactions will include preinfusion medication with methylprednisolone, paracetamol, and an H1-antihistamine before each daratumumab infusion. Methylprednisolone will also be administered after daratumumab infusions in Cycle 1 to prevent delayed infusion reactions.

The Follow-up Phase will begin once a subject completes the planned number of cycles and completes the End-of-Treatment visit within 4 weeks after last dose. Subjects who discontinue before disease progression must continue to have disease evaluations according to the Time and

Events Schedule. The Follow-up Phase will continue until death, lost to follow up, consent withdrawal, or study end, whichever occurs first.

Three data cutoff timepoints are planned:

- The first data cutoff is for an interim analysis 6 months after the last subject is randomized. This will be the basis for the analysis of the primary study endpoint of CR. All available data at the time of this data cutoff may be included in the interim analysis.
- The second data cutoff will occur 12 months after the last subject is randomized. This will be the basis for the analysis of the primary study endpoint of PD/death rate. All available data at the time of this data cutoff will be included in the Clinical Study Report.
- A third data cutoff will occur at the end of the study. The data collected will be reported as an addendum to the Clinical Study Report.

The end of the study will occur approximately 4 years after the last subject's first dose.

Assessment of tumor response and progression to multiple myeloma will be conducted in accordance with the International Myeloma Working Group (IMWG) criteria. An assessment of MRD will be conducted on whole blood and bone marrow aspirate samples. Safety evaluations will include AE monitoring, physical examinations, electrocardiogram (ECG) monitoring, clinical laboratory parameters (hematology and chemistry), vital sign measurements, and Eastern Cooperative Oncology Group (ECOG) performance status. A QTc substudy will be conducted in a subpopulation of subjects at selected sites. Blood samples will be drawn for assessment of pharmacokinetic and biomarker parameters.

1.3. Statistical Hypotheses for Trial Objectives

For each treatment arm, the following two hypotheses will be tested independently in each arm:

1. H_0 : CR rate $\leq 15\%$
 H_a : CR rate $\geq 35\%$
2. H_0 : PD/death rate $\geq 0.346/\text{patient-year}$ (median PFS < 24 months)
 H_a : PD/death rate $\leq 0.185/\text{patient-year}$ (median PFS > 45 months)

1.4. Sample Size Justification

This study will enroll 120 subjects (40/arm) in total. With 40 subjects per arm, each arm will have:

- 90% power to show that the true CR rate is 35% at a one-sided level of 0.05
- 80% power to show that the true PD/death rate is 0.185/patient year at a one-sided level of 0.1

If two or more treatment schedules are deemed to be effective, with 40 subjects per arm this study would have:

- 85% probability of identifying the arm with the higher CR

- 80% probability of identifying the arm with the lower PD/death rate

For the QTc substudy, assuming that the intrasubject standard deviation for change from baseline in QTc (Δ QTc) is 20 milliseconds and that the true difference in means is 5 milliseconds, a sample size of 25 evaluable subjects (completers) will have 80% power to show that the upper limit of the two-sided 90% confidence interval (1 sided upper 95% confidence interval) for the difference in mean QTc (Δ QTc) at each timepoint and baseline will be less than 20 milliseconds. To ensure 25 subjects are evaluable, the QTc substudy will enroll approximately 30 subjects.

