## 3.2. Study Design Rationale

### Rationale for Study Design

Randomization in the assignment of subjects to a dosing schedule will allow assessment of preliminary efficacy and safety across all 3 arms. To further minimize imbalance across treatment arms and to allow for important subgroup analyses, subjects will be stratified according to the number of risk factors present at screening ( $<2$  versus  $\geq 2$ ) using the criteria of Dispenzieri (2013). These risk factors will include: abnormal free light chain (FLC) ratio ( $<0.126$  or  $>8$ ), serum M-protein  $\geq 3$  g/dL, urine M-protein  $>500$  mg/24 hours, IgA subtype, and immunoparesis (at least 1 uninvolved immunoglobulin [IgG, IgA, IgM] decreased more than 25% below lower limit of normal [LLN]). Stratification factors will be based on central laboratory analyses.

The treatment effect, evaluating whether initial response will reduce the rate of progression to symptomatic MM or death in subjects with intermediate or high-risk SMM, will be measured using the endpoint of PFS, defined as the time between randomization and progression to symptomatic MM or death. Given that the median time to progression in the high-risk SMM patient population is about 2 years, assessment of PFS rate approximately 1 year after the last subject is randomized should provide an early indication of treatment effect. However, all subjects will continue to be followed, and in the final study analysis (expected up to approximately 7 years after the last subject's first dose), long-term data on PFS will be analyzed.

[figure not shown]
The criteria for efficacy (both response and follow up to progression to symptomatic MM, as defined by the IMWG, are objective and will be measured in all 3 treatment dosing schedules. The CR rate is defined as the proportion of subjects with CR. In a recent Phase 3 study of lenalidomide and dexamethasone in high-risk SMM patients, CR rate in the maintenance phase was 26% [Mateos 2013]. A correlation between CR and time to symptomatic MM has been demonstrated in simulation models conducted by the Janssen statistical team. A CR rate of 35% was chosen as the alternative hypothesis for this study, since a CR rate of at least 30% is considered to be most likely to translate into delay of progression to myeloma.

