### **11.3.1. Primary Efficacy Endpoint**

The primary efficacy endpoints are:

1. CR rate: The number and proportion of subjects who achieve a CR in each arm will be summarized. An exact 90% confidence interval and an exact p-value for rejecting the null hypothesis that the CR rate is 15% will be calculated.
2. PD/death rate: The ratio of subjects with an event (PD or death) to the total follow-up for all subjects will be summarized. A 90% confidence interval and a p-value for rejecting the null hypothesis that the PD/death rate is 0.346 will be calculated.

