2.5.1. Efficacy Analysis Set(s)

There are two primary efficacy analysis sets:

1. Response evaluable analysis set, defined as subjects who have measurable disease at baseline as per IMWG criteria (serum and urine, serum only, urine only, FLC) and received at least 1 dose of daratumumab treatment. In addition, subjects must have at least 1 post-baseline disease assessment. Analyses of the co-primary efficacy endpoint of complete response will be based on this population.
2. ITT analysis set, defined as subjects who have been randomly assigned to one of the 3 daratumumab schedules based on IWRS. Analyses of the co-primary efficacy endpoint of PD/death rate and secondary efficacy endpoints of progression-free survival (PFS), and overall survival (OS) will be based on this population.

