5. EFFICACY

5.1. Analysis Specifications

5.1.1. Level of Significance

For the co-primary endpoint of CR rate a 1-sided alpha of 0.05 will be used. For the co-primary endpoint of PD/death rate a 1-sided alpha of 0.1 will be used. No adjustments for multiplicity will be made.

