5.2.2. Analysis Methods

5.2.2.1. Complete Response

The number and percentage of subjects who achieve a complete response including 90% exact CI will be calculated for each treatment group based on response evaluable population. The exact p-value to test the hypothesis, H_0 : CR rate $\leq 15\%$ will also be calculated.

A similar analysis based on complete response based on investigator assessment will also be conducted.

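### The stated 90% power for CR is a modest overstatement: the exact test that the plan specifies has 87.9% power at 40 per arm

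*SAP*

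**What the plan says.** SAP 1.4 fixes the size, "This study will enroll 120 subjects (40/arm) in total", and claims for each arm "90% power to show that the true CR rate is 35% at a one-sided level of 0.05". Protocol 11.2 and the Synopsis make the same claim. None of the three names the formula behind the 90%.

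The planned analysis is exact. Protocol 11.3.1 says that "an exact p-value for rejecting the null hypothesis that the CR rate is 15% will be calculated", alongside an exact 90% confidence interval. SAP 5.2.2.1 likewise plans "The exact p-value to test the hypothesis" of a CR rate of 15% or less. The level comes from SAP 5.1.1: "For the co-primary endpoint of CR rate a 1-sided alpha of 0.05 will be used". SAP 1.3 applies the test separately in each arm, and SAP 5.1.1 adds "No adjustments for multiplicity will be made", so each arm has the full 0.05. The alternative comes from the design rationale in Protocol 3.2: "A CR rate of 35% was chosen as the alternative hypothesis for this study".

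SAP 2.5.1 defines a response-evaluable set: measurable disease at baseline, at least one dose and at least one post-baseline disease assessment. It then states: "Analyses of the co-primary efficacy endpoint of complete response will be based on this population". No allowance for non-evaluable subjects is given for CR, although the same sample size section makes one for the QTc substudy (about 30 enrolled to secure 25 evaluable).

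**The concern.** A stated power should describe the test that will be run. An exact binomial test on 40 subjects can reject only at whole-number cutoffs, so its attained alpha usually sits below 0.05 and its power can sit below what a smooth formula predicts. The same discreteness makes power sensitive to the exact number analysed, and under SAP 2.5.1 that number may be below 40.

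CR is a co-primary endpoint. Under Protocol 11.3 its analysis, six months after the last randomization, informs the choice of schedule and the decision on Phase 3. The figure at stake is the chance that an arm with a true CR rate of 35% fails its test. The cutoff is also not printed, so a reader cannot see that 25% observed CR (10 of 40) fails while 27.5% (11 of 40) succeeds.

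**Working it through.** **Inputs.** p0 = 0.15 (Protocol 11.3.1, SAP 5.2.2.1); p1 = 0.35 (Protocol 3.2, SAP 1.3); one-sided alpha 0.05 (SAP 5.1.1); n = 40 per arm (SAP 1.4); exact test, each arm separately (SAP 1.3, 5.2.2.1).

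**Step 1: where the 90% can come from.** Let se0 = sqrt(0.15 × 0.85 / 40) = 0.0565, se1 = sqrt(0.35 × 0.65 / 40) = 0.0754, z = 1.645, and Φ the standard normal distribution function.

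- Arcsine: Φ(2[asin √0.35 − asin √0.15] × √40 − 1.645) = Φ(0.4707 × 6.325 − 1.645) = Φ(1.332) = 90.9%.
- Normal with continuity correction: Φ((0.20 − 1.645 × 0.0565 − 1/80) / 0.0754) = Φ(1.255) = 89.5%.
- Normal without correction: Φ((0.20 − 1.645 × 0.0565) / 0.0754) = Φ(1.421) = 92.2%.
- Alternative variance only: Φ(0.20 / 0.0754 − 1.645) = Φ(1.007) = 84.3%.

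The first two agree with 90% after ordinary rounding.

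**Step 2: the planned exact test at n = 40.** Take the smallest r with P(X ≥ r | 40, 0.15) ≤ 0.05.

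- r = 10: P(X ≥ 10 | 40, 0.15) = 0.0672, too large.
- r = 11: P(X ≥ 11 | 40, 0.15) = 0.0299, allowed.

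The exact 90% confidence interval gives the same cutoff: its lower limit is 14.2% at 10 of 40 and 16.3% at 11 of 40.

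Power = P(X ≥ 11 | 40, 0.35) = 0.8785, or 87.9%. The shortfall is 90 − 87.9 = 2.1 points, and the chance of missing a true 35% rate is about 12.1% instead of 10%. A cutoff of 10 would give 93.6% power, but at an alpha of 0.067.

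**Step 3: fewer than 40 evaluable.** The documents give no non-evaluable rate. Assuming 0 to 6 per arm, with the cutoff re-derived for each n:

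| Evaluable n | Reject if CRs ≥ | Attained alpha | Power at 35% |
|---|---|---|---|
| 40 | 11 | 0.030 | 87.9% |
| 39 | 11 | 0.025 | 85.5% |
| 38 | 10 | 0.049 | 90.4% |
| 37 | 10 | 0.042 | 88.5% |
| 36 | 10 | 0.035 | 86.2% |
| 35 | 10 | 0.029 | 83.5% |
| 34 | 10 | 0.024 | 80.4% |

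The cutoff drops from 11 to 10 between n = 39 and n = 38, and power jumps up there. Above 40 the pattern is the same: 41 gives 89.8%, 43 gives 93.0%, 44 gives 89.3%, and power stays at or above 90% only from n = 45 (91.0%).

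**The case against.** The strongest reply is that the 90% is a planning figure, not a slip. The documents do not say that it came from the exact test, two standard formulas give about 90% at n = 40, and the smallest n with at least 90% exact power is 38, so 40 looks like that target with a small margin. The gap at 40 is a discreteness effect with a conservative attained alpha. This stands as an explanation and it keeps the point small. It does not make 90% the power of the specified test. Where the SAP wants an approximation it says so: SAP 5.2.2.2 names a normal approximation for the PD/death rate, whereas the CR test is called exact.

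A reader might also infer that using the response-evaluable set simply lowers power further. The table does not support that: power at 37 and 38 evaluable subjects exceeds power at 40. Nor do the documents support a claim that the evaluable number will usually be well below 40. Inclusion criterion 3.1 requires qualifying serum M-protein, urine M-protein or free light chain values, so most enrolled subjects are likely to have measurable disease. The loss of 0 to 6 per arm is an illustration, not an estimate.

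Finally, the exact p-value fixes the cutoff whether or not it is printed, so the analysis itself is not ambiguous. That is correct; the gain from printing it is transparency.

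**Conclusion.** The point holds as a minor one. For the exact one-sided 0.05 test at 40 per arm, power against a true CR rate of 35% is 87.9%, not 90%, with a cutoff of 11 and attained alpha 0.030. This part uses only the documents' own inputs. Over 34 to 40 evaluable subjects exact power runs between about 80% and 90%, non-monotonically, and reaches 90% at only one of those seven counts (38). That part rests on the assumed loss of 0 to 6 per arm.

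It would be too strong to call the 90% a miscalculation, since its method is unstated and approximations reproduce it. Nor is the test invalid: alpha is respected with room to spare. Protocol 11.1 assigns efficacy to the ITT population while SAP 2.5.1 uses the response-evaluable set for CR; that difference needs reconciling as a separate matter.

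**What to change.** In the Protocol Synopsis, Protocol 11.2 and SAP 1.4, replace the CR power statement with wording such as: *approximately 88% power by the exact binomial test when the true CR rate is 35% (reject if at least 11 of 40 subjects have a CR; attained one-sided alpha 0.030)*. Add one sentence saying that exact power ranges from about 80% to 90%, non-monotonically, for 34 to 40 response-evaluable subjects, and that the cutoff is re-derived from the number actually evaluable. If the sponsor has an expected non-evaluable rate, give it beside this range.

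The cost is wording only. The printed power becomes slightly less favourable; sample size, test and alpha are unchanged, and no extra patients are needed.

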1.5. Randomization and Blinding

Subjects will be randomized to treatment in a 1:1:1 ratio to either Treatment Arm A, Treatment Arm B, or Treatment Arm C. The method of randomization is randomly permuted blocks. An interactive web based randomization system (IWRS) will be used. Subjects will be stratified according to the number of risk factors present at screening (<2 versus ≥ 2) using the criteria of Dispenzieri (2013).¹ These risk factors will include: abnormal free light chain (FLC) ratio (<0.126 or >8), serum M-protein ≥ 3 g/dL, urine M-protein >500 mg/24 hours, IgA subtype, and immunoparesis (at least 1 uninvolved immunoglobulin [IgG, IgA, IgM] decreased more than 25% below lower limit of normal [LLN]). Stratification factors will be based on central laboratory analyses.

As this is an open label study, blinding procedures are not applicable.

2. GENERAL ANALYSIS DEFINITIONS

In general, continuous variables will be summarized using descriptive statistics such as mean, standard deviation, median and range. Categorical variables will be summarized using frequency and percentage. For time-to-event variables, which is defined as from randomization to the date of the event, the Kaplan-Meier method will be used for descriptive summaries.

2.1. Visit Windows

Any analysis that uses time-to-event data will be based on exact determination of time from randomization to the date of the event. For analyses of data by cycle, if data are collected by date (ie, AE onset), the corresponding study evaluations will be assigned to actual sequential cycles, which are derived from the study agent administration data. The start date of a particular cycle is defined as the date of the first scheduled dose, and the end date of a cycle is the start date of the next cycle minus 1. For the last cycle, the end date is defined as the end of treatment visit date or 55 days after the last dose if the end of treatment visit date is not available. If data (eg, laboratory and vital sign, etc) are collected by cycle, the nominal cycle will be used to summarize data.

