**Table 1: Time and Events Schedule Overview**

As of Amendment 5, refer to [Attachment 4](#) for a description of dose administration and study procedures for subjects who continue in the Treatment Extension Phase or who have discontinued treatment but remain in Follow-up.

|   |  | Screening Phase                     | Treatment Phase (including treatment extension/re-initiation phase)                      | EOT                            | Follow-up |
|---|--|-------------------------------------|--|--------------------------------|-----------|
|   | Notes  | within 28 days before randomization | 8-week cycles  | at 28 ± 7 days after last dose |           |
| Study treatment should be initiated within 5 days after randomization. The start of each cycle may occur ±5 days of the scheduled day in order to accommodate the schedule of the site or subject. After EOT, subjects in all treatment arms prior to PD will continue to return for disease evaluations. After PD is documented, subjects will be followed for survival; subsequent anticancer therapy, and occurrence of other malignancy. Follow-up visits, unless otherwise specified, are at Week 5, Week 9, and then q8wks during the first year after subject's first dose, then q16wks until PD and q6mos after PD. |  |                                     |  |                                |           |
| Procedures   |  |                                     |  |                                |           |
| Informed consent  | ICF must be signed before any study-related procedures are performed.  | X                                   |  |                                |           |
| Eligibility criteria  |  | X                                   |  |                                |           |
| Demography/
Medical History  |  | X                                   |  |                                |           |
| Chest X-ray   | Acceptable for screening if performed as part of SOC within 42 days before randomization   | X                                   |  |                                |           |
| FEV1 test   | Subjects with COPD   | X                                   |  |                                |           |

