**Table 3: Time and Events Schedule, Dose Administration**

As of Amendment 5, refer to [Attachment 4](#) for a description of study drug administration and study procedures for subjects who continue in the Treatment Extension Phase or who have discontinued treatment but remain in Follow-up.

|   |  | C1   |    |     |     |     |     |     |     | C2 and C3 |     |     |     | C4-C7 |     | C8-C20
(including
treatment
extension/
re-initiation
phase) | EOT |
|---|--|--|----|-----|-----|-----|-----|-----|-----|-----------|-----|-----|-----|-------|-----|--|-----|
|   |  | D1   | D8 | D15 | D22 | D29 | D36 | D43 | D50 | D1        | D15 | D29 | D43 | D1    | D29 | D1   |     |
| Study Drug Administration. Refer to Site investigational Product Procedures Manual for recommendations on daratumumab infusion rate. |  |  |    |     |     |     |     |     |     |           |     |     |     |       |     |  |     |
| Arm A   |  | X  | X  | X   | X   | X   | X   | X   | X   | X         | X   | X   | X   | X     | X   | X  |     |
| Arm B   |  | X  | X  | X   | X   | X   | X   | X   | X   | X         |     |     |     | X     |     | X  |     |
| Arm C   |  | X  | X  | X   | X   | X   | X   | X   | X   |           |     |     |     |       |     |  |     |
| Pre-infusion Medications   |  |  |    |     |     |     |     |     |     |           |     |     |     |       |     |  |     |
| Methylprednisolone  | Methylprednisolone 100 mg for first 2 infusions, 60 mg for all subsequent infusions. Substitutions allowed, see Attachment 3 . | approximately 1 hr prior to every infusion of daratumumab                                    |    |     |     |     |     |     |     |           |     |     |     |       |     |  |     |
| H1-antihistamine  | Diphenhydramine 25-50 mg, cetirizine 10 mg, or equivalent  | approximately 1 hr prior to every infusion of daratumumab                                    |    |     |     |     |     |     |     |           |     |     |     |       |     |  |     |
| Paracetamol   | Paracetamol or acetaminophen 650-1000 mg   | approximately 1 hr prior to every infusion of daratumumab                                    |    |     |     |     |     |     |     |           |     |     |     |       |     |  |     |

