### End of Treatment Visits

Unless a subject withdraws consent for study participation or is lost to follow up, an End-of-Treatment Visit is to occur at 28 days  $\pm 7$  days after the last dose of all study treatments. Every effort should be made to conduct the End-of-Treatment Visit before the subject starts subsequent treatment. If a subject is unable to return to the site for the End-of-Treatment Visit, then the subject should be contacted to collect information on AEs and concomitant medications that occur up to 30 days after the last dose of study treatment. Additional information on reporting of AEs is presented in [Section 12](#). Due to the addition of the treatment extension outlined in Amendment 4 which allowed some subjects to resume daratumumab treatment if within 6 months of last dose of Cycle 20, it is possible for subjects to have 2 EOT visits associated with this study. As of Amendment 5, this additional EOT visit associated with treatment extension should be conducted as specified in [Attachment 4](#).

As such, 2 EOT visit CRFs should be completed as applicable for subjects who continued to treatment extension (End of Treatment CRF and End of Treatment Extension CRF).

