6.3.2. Infections and Infestations

Infections and infestations refer to adverse events with MedDRA SOC of infections and infestations. A summary of number of subjects with 1 or more toxicity Grade 3 or 4 treatment-emergent infections and infestations by MedDRA preferred term and relationship to treatment will be provided. In addition, incidences of Grade 3 or 4 treatment-emergent infections and infestation will be summarized by MedDRA preferred term and treatment cycle.

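### The SAP's last-cycle rule makes Arm C's Cycle 1 about 78 days long against 56 in Arms A and B, so the infection-by-cycle table does not compare equal windows

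*SAP*

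**What the plan says.** SAP 2.1 (Visit Windows) places data collected by date, with adverse event onset as its example, into actual cycles derived from the dosing records. For any cycle that is followed by another, "the end date of a cycle is the start date of the next cycle minus 1". For the final one, "For the last cycle, the end date is defined as the end of treatment visit date or 55 days after the last dose", where the 55-day option is the fallback if no EOT visit date is available.

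SAP 1.2 states "Treatment cycles are 8 weeks in length" and "For subjects randomized to Arm C, the Treatment Phase consists of Cycle 1 only, when daratumumab will be administered weekly". In Protocol Table 3 the Cycle 1 columns after Day 1 are "D8 | D15 | D22 | D29 | D36 | D43 | D50", and all three arms are marked for dosing on every one of them. Protocol Table 1 puts the EOT visit "at 28 ± 7 days after last dose"; the protocol text on End of Treatment Visits agrees ("an End-of-Treatment Visit is to occur at 28 days", with the same 7-day tolerance).

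The output that uses these windows is in SAP 6.3.2: "incidences of Grade 3 or 4 treatment-emergent infections and infestation will be summarized by MedDRA preferred term and treatment cycle". SAP 6 presents safety results by treatment received. SAP 6.1 counts an event as treatment-emergent up to 30 days after the last dose, or later if it is judged drug-related.

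**The concern.** Cycle 1 is the only interval in which the three arms follow the same planned dosing, and describing the safety of the three schedules is a secondary objective (SAP 1.1). A reader of an infection-by-cycle table will naturally compare the Cycle 1 column across arms. For Arm C, Cycle 1 is also the last cycle, so the last-cycle rule closes it. For Arms A and B the start of Cycle 2 closes it. The same column heading then covers windows of different length.

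Nothing in the SAP truncates Arm C at Day 56, adjusts for time at risk, or asks for days at risk to be shown. If infections occur at all between Day 57 and the EOT visit, Arm C's Cycle 1 cell collects them. In Arms A and B, infections in the same calendar interval go to Cycle 2. The table itself gives no sign of this.

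**Working it through.** **Inputs.** Cycle length 8 weeks (SAP 1.2). Cycle-end rules (SAP 2.1). Last planned Cycle 1 dose on Day 50 (Protocol Table 3). EOT at last dose + 28 ± 7 days (Protocol Table 1). Treatment-emergent limit at last dose + 30 days (SAP 6.1). 40 subjects planned per arm (SAP 1.2). The infection rate over time is not in the documents, so it is varied below as an assumption.

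**Step 1: reproduce the stated cycle length.** In Arms A and B, Cycle 2 starts on nominal Day 57, so Cycle 1 ends on Day 57 − 1 = 56. That is 56 days = 8 × 7, which matches the SAP.

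**Step 2: Arm C, subjects who receive the Day 50 dose.**

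| How Cycle 1 closes | End day | Ratio to 56 | Ratio with the Day 80 limit |
|---|---|---|---|
| EOT 7 days early | 50 + 21 = 71 | 1.27 | 1.27 |
| EOT on the nominal day | 50 + 28 = 78 | 1.39 | 1.39 |
| EOT 7 days late | 50 + 35 = 85 | 1.52 | 80/56 = 1.43 |
| EOT date missing | 50 + 55 = 105 | 1.88 | 80/56 = 1.43 |

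The limit is Day 50 + 30 = 80 and does not apply to events judged drug-related. SAP 1.2 words the EOT timing as within four weeks of the last dose, which would put it at Day 78 at the latest.

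The 55-day fallback closes a cycle at 56 days exactly when the cycle's last dose falls on Day 1 (1 + 55 = 56). Counted from Day 50 it gives 105.

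**Step 3: effect on incidence.** Let p be the 56-day incidence and h the hazard in Days 57–78 relative to Days 1–56. Then Arm C shows p_C = 1 − (1 − p)^((56 + 22h)/56).

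With a constant hazard (h = 1) the exponent is 78/56:

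| p | p_C | Relative excess | Expected subjects of 40 |
|---|---|---|---|
| 1% | 1.39% | 39% | 0.4 to 0.56 |
| 5% | 6.9% | 38% | 2.0 to 2.76 |
| 10% | 13.6% | 37% | 4.0 to 5.46 |
| 20% | 26.7% | 34% | 8.0 to 10.69 |

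With p = 5% and other values of h, the relative excess is 0% (h = 0), 10% (h = 0.25), 19% (h = 0.5) and 57% (h = 1.5).

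**Step 4: with the change proposed below.** Arm C's Cycle 1 ends on Day 1 + 55 = 56, so the ratio is 56/56 = 1.00. Days 57 to 80 become a separate post-treatment interval.

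**The case against.** The best defence is that the consequence is small. Cycle assignment by onset date feeds one named adverse event output, the by-cycle sentence in SAP 6.3.2. That output is descriptive and no test depends on it. The main summaries of adverse events, serious events and Grade 3 or 4 events are not by cycle, and data collected by cycle, such as laboratory values and vital signs, use the nominal cycle. At 5% incidence the difference is 0.8 of a subject in 40, which the table then splits by preferred term. The SAP never names Cycle 1 as a between-arm comparison. Running Arm C's only cycle to the EOT visit also keeps most of its post-dose events inside a cycle, which is a defensible choice if footnoted. All of this stands. It limits the weight of the point but does not make the windows equal.

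Three stronger readings are tempting, and the documents do not support them.

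- A reader might infer that the table overstates Arm C infections by about 40%. The 39% is a ratio of window lengths. Turning it into incidence needs a constant hazard over Days 1 to 78, and the documents give no rate over time.
- A reader might infer that the rule also halves the final cycle of subjects dosed every 8 weeks, because EOT falls on about Day 29 of that cycle. The 30-day treatment-emergent limit would stop most counting at Day 31 anyway, so SAP 2.1 accounts for about two days.
- A reader might infer that anyone stopping early in a weekly or two-weekly cycle gets an over-long window. With EOT 28 days after the last dose, stopping after the Day 1, 8, 15 or 22 dose closes the cycle on Day 29, 36, 43 or 50, all shorter than 56.

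**Conclusion.** The point holds for window length. For subjects who receive the Day 50 dose, Arm C's Cycle 1 is about 78 days against 56, or 39% longer. The range is 27% to 43% once the EOT window and the Day 80 limit are applied. This rests only on the documents' own rules and nominal visit days.

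The effect on infection incidence is conditional. It is 34% to 39% higher under a constant hazard for 56-day incidences of 1% to 20%. At 5% it is anywhere from 0% to 57% if the later hazard is 0 to 1.5 times the earlier one. The Cycle 1 column of a planned safety display by schedule is not like-for-like, and the cause is a rule that is easy to change. No primary or secondary efficacy result is touched.

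**What to change.** In SAP 2.1, leave the rule for every non-last cycle as it is. Cycle starts may move by ± 5 days and doses may be delayed (Protocol 6 and 6.5). Capping all cycles at 56 days would leave on-treatment days belonging to no cycle.

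For the last cycle only, end it at that cycle's first dose date + 55 days, or at the last dose date if that is later. Put treatment-emergent events after that date in a separate post-treatment column. In each cycle column show the number of subjects and the days at risk, counting days only while the subject is inside the treatment-emergent period. Subjects who stop part-way through a cycle are then also shown with their true time at risk.

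The cost is a sentence or two in the SAP, a small change to the derived cycle variable and one extra table column. No new data are needed.
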